## 2.7 Safety analyses

For all safety analyses, the safety set will be used.

Safety summaries (tables, figures) will include only treatment emergent adverse events (i.e. adverse events started after the first dose of study treatment or adverse events that were present prior to start of study treatment but increased in severity during the course of the study). Listings will include all data.

Vital signs values that have complete data and time values will be allocated to pre- or post-dose assessment (as per protocol) based on the actual date/time. For values with missing date/time, scheduled visit date and time will be used. This rule will be applied to data from scheduled visits only. If a measurement scheduled as pre-dose is actually performed post-dose, or vice versa, the data will not be used for by visit/time point summary.

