10.2 Reporting requirements for adverse events

In this study, only SAEs will be detected, documented and reported. AEs leading to treatment discontinuation will be documented.

- The investigator or delegate has the responsibility for managing the safety of individual participants and identifying and reporting events that meet the definition of AE leading to treatment discontinuation, and SAEs.
- Novartis qualified medical personnel will be readily available to advise on trial related medical questions or problems.
- NWEH's ConneXon trials platform will be utilised for remote safety monitoring. Using this technology all SAEs will be alerted to the study team. SAEs will be reported to the sponsor within 24 hours of awareness.
- AEs also may be detected when they are volunteered by participants during or between visits or other assessments such as when the patient reported outcomes questionnaires (CSQ-8, PAM (CSQ-8, PAM)) are returned to the study team (see 16.2 Appendix 2: The CSQ-8 PROMs Questionnaire, 16.3 Appendix 3: The PAM PROMs Questionnaire and 16.4 Appendix 4:).

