10.3 Collection and assessment of adverse events

10.3.1 Adverse event severity

The severity of AE will be assessed by the investigator or delegate.

- mild: usually transient in nature and generally not interfering with normal activities
- moderate: sufficiently discomforting to interfere with normal activities
- severe: prevents normal activities

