12.5.2 Safety endpoints

For all safety analyses, the safety set will be used. All tables will be presented by treatment group.

Safety summaries (tables, figures) include only treatment emergent events (events started after the first dose of study medication or events present prior to start of double-blind treatment but increased in severity based on preferred term) with the exception of baseline data which will also be summarised where appropriate (e.g. change from baseline summaries). In addition, a separate summary for deaths including on treatment and post treatment deaths will be provided.

In particular, summary tables for adverse events (AEs) will summarise only treatment emergent AEs.

Adverse events

The number (and percentage) of participants with serious adverse events and treatment emergent adverse events leading to discontinuation (started after the first dose of study medication) will be summarised in the following ways:

- by treatment, primary system organ class and preferred term.
- by treatment, primary system organ class, preferred term and maximum severity.
- by treatment, Standardised MedDRA Query (SMQ) and preferred term.

Separate summaries will be provided for study medication related adverse events, death, serious adverse events, other significant adverse events leading to discontinuation.

A participant with multiple adverse events within a primary system organ class is only counted once towards the total of the primary system organ class.

Adverse events which will be counted for a specific treatment period are those which are treatment-emergent. These events are those with an onset after the start of the treatment period, or which were present prior to the start of the treatment period but increased in severity, changed from being not suspected to being suspected of study drug relationship, or developed into SAEs after the start of the treatment period.

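### SAP 2.7 adopts the narrower of two conflicting treatment-emergent definitions in protocol 12.5.2, so some pre-dose-onset events that become serious or suspected after dosing can miss the SAE and registry tables

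*SAP*

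**What the plan says.** SAP 2.7 sets the filter for every safety output: "Safety summaries (tables, figures) will include only treatment emergent adverse events". An event qualifies if it started after the first dose, or if it is one of the "adverse events that were present prior to start of study treatment but increased in severity during the course of the study". Listings are exempt: "Listings will include all data". SAP 2.7.1 builds the clinicaltrials.gov and EudraCT tables on treatment-emergent SAEs. SAP Section 1 says the data will be analysed according to protocol Section 12.

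Protocol 12.5.2 defines treatment-emergent twice. The opening text on safety summaries admits events that began after the first dose and "events present prior to start of double-blind treatment but increased in severity based on preferred term". The closing paragraph, on which events are counted for a treatment period, keeps onset and severity but adds events that "changed from being not suspected to being suspected of study drug relationship, or developed into SAEs after the start of the treatment period".

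On collection, protocol 10.2 says: "In this study, only SAEs will be detected, documented and reported. AEs leading to treatment discontinuation will be documented". For recorded events, protocol 10.3.1 says: "The severity of AE will be assessed by the investigator or delegate". Section 10.3.2 requires changes in severity to be followed once an event is detected. Section 10.3.3 collects SAEs from consent until 30 days after the end-of-study visit.

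**The concern.** The serious adverse event profile is a stated secondary objective (protocol 3.2). Two programmers, one working from SAP 2.7 and the other from the closing paragraph of protocol 12.5.2, could produce different counts from the same data.

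The omitted parts matter more here than in a trial that records all adverse events. With full recording, an event already present before the first dose has a grade, and later worsening can be shown against it. In this trial a non-serious event between consent and first dose normally leaves no adverse event record, so the severity criterion often has no comparator. Severity and seriousness are also different attributes: protocol 10.3.1 grades interference with normal activities, while 10.1.2 defines seriousness by outcomes such as inpatient admission. An event can become serious without a change of grade. Any resulting error goes one way, because the narrower rule can remove events from the tables but cannot add them.

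**Working it through.** **Definitions side by side**

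| Criterion for an event present before the first dose | Protocol 12.5.2, opening | Protocol 12.5.2, closing | SAP 2.7 |
|---|---|---|---|
| Increased in severity | yes | yes | yes |
| Changed from not suspected to suspected | no | yes | no |
| Developed into an SAE | no | yes | no |

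**An event that began before dosing and became serious after it**

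1. The SAE is entered with the worsening as its onset. The SAE definition in protocol 10.1.2 includes worsening of a pre-existing condition, so this is possible. Onset is then after the first dose and SAP 2.7 keeps the event.
2. The pre-dose onset is kept and a rise in grade is recorded. SAP 2.7 keeps the event through the severity criterion.
3. The pre-dose onset is kept and no rise in grade is recorded, because there was no earlier grade or because the grade is unchanged but the participant is now in hospital. SAP 2.7 drops the event from the tables; the closing paragraph of protocol 12.5.2 keeps it.

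Only route 3 is lost. Neither document says whether a worsening takes a new onset date, so the split between routes 1 and 3 is left to the person completing the form.

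**An SAE that began before dosing and became suspected after it**

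Under protocol 10.3.3, progression of an SAE is reported as follow-up to the original episode, so the pre-dose onset stays. If the grade does not rise, SAP 2.7 drops the event and the closing paragraph of 12.5.2 keeps it.

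**Illustration of size (route 3 only)**

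The documents give no SAE rate, no mean gap from consent to dose, and no proportion of events turning serious late. The assumptions are:

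- 10 to 20 SAEs per 100 patient-years;
- a mean gap of 7 to 14 days (protocol 8.2 has screening within 14 days before treatment, so 14 is the nominal maximum and 7 is what a uniform spread would give);
- 10% to 50% of SAEs with pre-dose onset becoming serious only after dosing.

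The two inclisiran groups have 2 × 300 = 600 participants.

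- Time in the gap: 600 × 7/365 = 11.5 to 600 × 14/365 = 23.0 patient-years.
- SAEs with pre-dose onset: 11.5 × 0.10 = 1.2 to 23.0 × 0.20 = 4.6.
- Of these, serious only after dosing: 1.2 × 0.10 = 0.1 to 4.6 × 0.50 = 2.3.
- For comparison, SAEs over 270 + 30 = 300 days: 600 × 300/365 = 493 patient-years; × 0.10 to 0.20 = 49 to 99.

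The SAE rate cancels from the relative loss, which is 7 × 0.10/300 = 0.2% to 14 × 0.50/300 = 2.3%. Events kept by routes 1 and 2 have not been subtracted, so these figures lean high. Table 8-1 allows Day 1 to be up to 14 days late, so one participant's gap could reach about 14 + 14 = 28 days, but that is an extreme and not a plausible mean.

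**The case against.** The strongest reply is that the SAP does follow the protocol. The opening of 12.5.2 states the rule for safety tables and figures, and SAP 2.7 repeats it for the same outputs; the broader text speaks of events counted for a treatment period. A reader might infer that the SAP simply departs from the protocol, and the documents do not support that: the conflict starts inside 12.5.2. It still has to be resolved. Table 8-1 has a single treatment period, so the two paragraphs address the same events. The opening one also refers to double-blind treatment in an open-label trial, which suggests it was not fully adapted to this study.

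A reader might also infer that a severity increase cannot be observed in this trial. That goes too far. Severity is graded, changes are followed once an event is detected, and maximum severity is tabulated (SAP 2.7.1). What is missing is the pre-dose grade of a non-serious event.

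Nor does every event that turns serious after dosing leave the SAE tables. Exclusion needs a retained pre-dose onset and no recorded rise in grade. Partial onset dates in the month of first dose are normally imputed to after dosing (SAP 5.1.2.1).

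Finally, safety oversight does not depend on this filter: SAEs are reported to the sponsor from consent onwards whether or not they are treatment-emergent, and deaths have their own summary. This limits the consequence to tabulated and registry counts.

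**Conclusion.** The point holds as an inconsistency with a small, one-directional effect. SAP 2.7 takes the narrower of two protocol definitions and omits both the causality and the SAE criteria. Events with a retained pre-dose onset that become serious or suspected after dosing, without a recorded increase in grade, leave the SAE and registry tables and stay in the listings.

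The number is probably very small and cannot be derived from the documents. The illustrative 0 to 2 events rest entirely on the assumed SAE rate, gap and late-seriousness proportion, and cover only the SAE criterion. The case for acting rests on having one definition and on removing an error that can only lower the counts. It does not rest on an expected shift in the safety conclusions.

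**What to change.** Before database lock:

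- Put the full closing definition of protocol 12.5.2 into SAP 2.7, with both the causality and the SAE criteria.
- Align the opening paragraph of protocol 12.5.2 with it, so that one definition stands in both documents.
- State that an event with pre-dose onset that first meets a seriousness criterion after the first dose counts as treatment-emergent. Use the date of seriousness if it was collected; otherwise use the available SAE report or hospitalisation information.

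The third step is conditional because protocol 10.3.2 asks for start and end dates and the seriousness criteria met, but does not list a date on which the event became serious. All 900 participants had been randomised by 15 July 2022 according to Amendment 2, so a field that was not collected would have to be reconstructed from existing records. That review is confined to SAEs with pre-dose onset.

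The cost is a wording change in each document and one derivation, plus that review if the date is missing. The downside is that the treatment-emergent SAE count may rise slightly.

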#### 2.7.1 Adverse events (AEs)

The number (and percentage) of participants with TEAEs will be summarized by treatment groups and overall in the following ways:

- By treatment, primary system organ class (SOC) and preferred term (PT).
- By treatment, primary system organ class (SOC), PT and maximum severity.
- By treatment, Standardized MeDRA query (SMQ) and PT.

Separate summaries will be provided for study medication related adverse events, death, serious adverse events, other significant adverse events leading to treatment discontinuation.

Unless otherwise specified, SOCs will be sorted alphabetically and, within each SOC, the PTs will be sorted in descending order of frequency in the total column. A participant with multiple

| Novartis | Confidential | Page 23 of 37           |
|----------|--------------|-------------------------|
| SAP      |              | Study No. CKJX839A1GB01 |

adverse events within the same PT, the AE will be counted only once. A participant with multiple adverse events within a primary system organ class is only counted once towards the total of the primary system organ class. In case of summary by severity or relationship to study drug, summary will be done using the most severe or related occurrence respectively. Listing of all AEs and SAEs will be provided.

**AE reporting for CT.gov and EudraCT**: For the legal requirements of clinicaltrials.gov and EudraCT, two required tables on treatment emergent adverse events which are not serious adverse events, on treatment emergent serious adverse events and SAE suspected to be related to study treatment will be provided by system organ class and preferred term on the safety set population.

If for a same patient, several consecutive AEs (irrespective of study treatment causality, seriousness and severity) occurred with the same SOC and PT:

- a single occurrence will be counted if there is ≤ 1 day gap between the end date of the preceding AE and the start date of the consecutive AE
- more than one occurrence will be counted if there is > 1 day gap between the end date of the preceding AE and the start date of the consecutive AE

For occurrence, the presence of at least one SAE / SAE suspected to be related to study treatment / non SAE has to be checked in a block e.g., among AE's in a  $\leq 1$  day gap block, if at least one SAE is occurring, then one occurrence is calculated for that SAE.

The number of deaths resulting from SAEs suspected to be related to study treatment and SAEs irrespective of study treatment relationship will be provided by SOC and PT.

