	Group 3: Participants will continue to receive their background lipid lowering therapy, plus inclisiran for injection (delivered in an injection-only model), plus behavioural support.	
Efficacy assessments	A capillary blood sample will be taken for immediate analysis of the participant's lipid profile for assessment of efficacy. This will be performed at screening/baseline visit, day 90 and end of study (EOS) visit.	
	 Parameters to be assessed include: Non-HDL (calculated) LDL-C calculated using Friedewald 	
Key safety assessments	Adverse events will be collected throughout the study period using ConneXon data platform.	
	The AEs to be recorded are:	
	 All SAEs whatever the causal relationship to the to the Investigational Medicinal Product (IMP) or to a procedure required by the study protocol AEs leading to treatment discontinuation 	
Other assessments	Comparisons between the Group 2 and 3 and the different delivery models will analyse whether the 'supported inclisiran' arm generates greater benefits than the injection only model in terms of outcomes other than LDL cholesterol: patient adherence, acceptability (both through PROMs) and wider cardiovascular risk. A process evaluation will build on and extend the study results, providing in-depth data on adherence and acceptability (through detailed interviews) with patients and professionals involved in the trial.	
Data analysis	The primary effectiveness objective of this study is to demonstrate superiorit each inclisiran arm compared to standard of care + behavioural support in te of the percentage change from baseline in LDL-C to Day 270 in adults elevated LDL-C. The statistical hypotheses that will be tested for each inclis arm are as follows:	
	• H0: The difference between participants treated with inclisiran (+/- behavioural support) and standard of care + behavioural support in the least squares mean percentage change from baseline to the Day 270 visit in LDL-C= 0	
	 Ha: The difference between participants treated with inclisiran (+/- behavioural support) and standard of care + behavioural support in the least squares mean percentage change from baseline to the Day 270 visit in LDL-C < 0 	

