In Phase II study MDCO-PCS-15-01 (ORION-1), clinically relevant injection site reactions were reported in a total of 13 (3.5%) inclisiran-treated subjects and no subjects (0.0%) in the placebo group following a single dose (single and double dose groups combined) through Day 90. Injection site reactions were reported in a total of 6 (3.4%) inclisiran-treated subjects and no subjects (0.0%) in the placebo group following a second dose. No observed difference or dose relationship was observed between inclisiran groups. The frequency of injection site reactions was similar after a second dose of inclisiran (3.4%) to that observed after the first dose (3.5%). All AEs at the injection site resolved without sequelae with the exception of one subject who received a single dose of inclisiran sodium 300 mg on Day 1 and continued to have a 2 mm erythema spot at the injection site on Day 210.

Novartis	Confidential	Page 26 of 85
CLINICAL TRIAL PROTOCOL: Version 02	Protocol No. CKJX839A1GE	301 (VICTORION Spirit)

In the Phase III studies MDCO-PCS-17-03 (ORION-9), MDCO-PCS-17-04 (ORION-10) and MDCO-PCS-17-08 (ORION-11), more inclisiran-treated subjects, 8.2% (150/1833), reported at least one Treatment Emerged Adverse Events (TEAE) at the injection site than placebo-treated subjects 1.8% (33/1822). Of the 183 subjects with a TEAEs at the injection site, the majority had a mild event (4.2%; 154/3655 subjects) and none had a severe event. No inclisiran-treated subject had a serious TEAE at the injection site. Four (4) inclisiran-treated subjects withdrew from study drug due to non-serious TEAEs at the injection site.

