The questionnaires will be returned to NWEH's research office in a stamped addressed envelope, for transcription into the eCRF. The questionnaires will be reviewed for completeness by the study team and participants contacted to ascertain any missing responses, the data will then be transcribed on to the eCRF. Unreturned questionnaires will be followed up twice at 2-weekly intervals.

Quantitative and qualitative methods (see Section 4.3) will be used to explore patient experience and adherence to the different models of care.

These will be based on existing validated PROMS questionnaires used for other conditions (see Appendix 4).

Any adverse events reported on a returned questionnaire will be assessed against the SAE reporting criteria for this study (Section 10) by the investigator or delegate and reported accordingly.

NWEH's ConneXon trials platform will be utilised for remote safety monitoring with minimal intervention, thereby reducing patient visits and maintaining real-world conditions for participants. Using this technology all **series** and serious adverse events (SAEs) will be alerted to the study team and reported to the sponsor within 24 hours of awareness.

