8.1 Domiciliary visits

In the event of a global health disruption event, such as a pandemic/epidemic (e.g. COVID-19), that limits or prevents the conduct of site study visits per protocol, special effort should be made to conduct on-site visits. If it is not feasible to conduct on-site visits, visits to the patient's home can be attempted. These visits will be performed by experienced HCPs with anaphylaxis training and following local guidelines and SOPs.

Period	Screening	Treatment		
Visit Name	Screening/	Treatment Period		End of Study
	Baseline			
Day	(-14 to -1)	Day 1 (± 14 days)	Day 90 (± 14 days)	Day 270 (± 14 days)
Obtain informed consent	Х			
Demography	Х			
Inclusion/exclusion criteria	Х			
Relevant / current medical history ¹				
Height	Х			Х
Smoking Status	X			Х
Dietary advice status	Х			Х
Exercise status	Х			Х
HbA1c ²	Х			Х
Lipid profile	Х		Х	Х
Urine pregnancy test for WOCBP	Х			
Adverse Events ⁴	X			
Prior/Concomitant Medications ⁵				

Table 8-1Assessment schedule

Period	Screening	Trea		
Visit Name	Screening/	Treatment Period		End of Study
	Baseline			
Day	(-14 to -1)	Day 1 (± 14 days)	Day 90 (± 14 days)	Day 270 (± 14 days)
Patient Reported Outcomes (PAM) ⁶	Х		Х	
Patient Reported Outcomes (CSQ-8) ⁶		X		
Behavioural Support Programme ⁷		Participants in the inclisiran + behavioural support and standard of care + behavioural support arms will have access to this service throughout the study		
Process Evaluation ⁸				
Study drug administration		Х	Х	
IWRS/IRT Registration/Randomisation	Х	X ¹⁰ X X		

X = assessment to be recorded in the clinical database or received electronically from a vendor

¹ ConneXon Data Platform to automate regular collection from EMR.

² ConneXon Data Platform to automate collection of closest recorded value prior to the screening/baseline visit and EOS visit.

³ Capillary sample to be taken for immediate analysis using a CardioChek device for analysis of lipid profile

LDL-C and non-HDL).

⁴ After screening/baseline visit all SAE's will be monitored and collected using ConneXon Data Platform (see Section 10).

⁵ Use of ConneXon Data Platform to automate regular collection from EMR.

^PThe behavioural support programme consists of a telephone based support service providing advice on diet, lifestyle, medication adherence, and DV risk management. Patients will have access to a scheduled programme of delivery

⁸ Process Evaluation interviews will be carried out in line with the study visits at Day 1 and Day 90.

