#### 2.7.1.1 Adverse events of special interest / grouping of AEs

Adverse event of special interest (AESI): The number and percentage of participants who reported TEAEs of special interest will be summarized by PT, treatment group. PTs will be sorted in descending order of frequency in the total column. If a participant reported more than one adverse event with the same PT, the AE will be counted only once. If a participant reported more than one AE within the same AESI, the participant will be counted only once at that AESI. Listing of participants with adverse event of special interest will be provided.

The Compound Case Retrieval Strategy (CRS) will be used to determine the MedDRA search criteria to be used to identify events of special interest.

Adverse event of special interest will include the following:

- Hepatotoxicity (Hepatic events)
- New onset or worsening of diabetis mellitus

For search criteria of AE of special interest, refer to Appendix 5.3.

| Novartis | Confidential | Page 24 of 37           |
|----------|--------------|-------------------------|
| SAP      |              | Study No. CKJX839A1GB01 |

The most recent list of adverse events of special interest at the time of database lock will be used. CRS listing will be provided.

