## 5.3 Search criteria for AE of special interest

The Adverse events of special interest (AESIs) based on MedDRA terms are defined in the Case Retrieval Strategy (eCRS). To select the corresponding records from SAS dataset ECRS in Novartis computing environment, use

- Compound name (DRGNAM)="KJX839",
- Compound indication (DRGINDC)="Hypercholesterolemia",
- Records with MDRAVER = 25.0

| Novartis | Confidential | Page 30 of 37           |
|----------|--------------|-------------------------|
| SAP      |              | Study No. CKJX839A1GB01 |

Safety topics flagged in the eCRS using the safety flag (PSURFL =YES) will be filtered and further safety topics mentioned in section 2.7.1.1 will be considered for analyses.

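### The SAP tabulates all TEAEs, non-serious TEAEs and AESIs, but the protocol collects only SAEs and AEs that lead to treatment discontinuation, so the tables need restricting and relabelling

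*SAP*

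**What the plan says.** **What is collected.** Protocol 10.2: "In this study, only SAEs will be detected, documented and reported. AEs leading to treatment discontinuation will be documented". The protocol summary names the same two categories, the second being "AEs leading to treatment discontinuation". Table 8-1, footnote 4, mentions only the serious ones: "After screening/baseline visit all SAE's will be monitored and collected using ConneXon Data Platform". Events written on patient questionnaires go through the same filter (Protocol 4.5): "Any adverse events reported on a returned questionnaire will be assessed against the SAE reporting criteria for this study". Under SAP 2.7.3 a laboratory abnormality becomes an AE only if it leads to discontinuation; Protocol 8.6 adds those that meet the SAE definition.

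**What the protocol tabulates.** Section 12.5.2 lists counts and percentages of participants with SAEs and with TEAEs leading to discontinuation.

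**What the SAP tabulates.** For the SAE-profile objective, the SAP 1.2 endpoint is the incidence, severity and relatedness of TEAEs in general, alongside SAEs and AEs leading to discontinuation. SAP 2.7.1 summarises all TEAEs by system organ class and preferred term, by maximum severity and by SMQ. For clinicaltrials.gov and EudraCT it adds "two required tables on treatment emergent adverse events which are not serious adverse events", along with serious and suspected serious events. SAP 2.7.1.1 gives numbers and percentages for two AESIs: hepatic events and "New onset or worsening of diabetis mellitus". No visible text in these sections states the collection limit.

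**Dictionary version.** SAP 5.2 codes AEs in the MedDRA version available at database lock. SAP 2.7.1.1 uses the AESI list current at lock. SAP 5.3 selects "Records with MDRAVER = 25.0".

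**The concern.** A table of participants with an event, divided by the full Safety Set, reads as an incidence. It is one only if the event was looked for and recorded whenever it occurred. Here a non-serious event reaches the AE dataset, apart from minor routes, only if it led to discontinuation of inclisiran. The SAP tables are broader than the data behind them, and a reader of the CSR or registry entry would not learn this from the table itself.

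The gap matters most for the one reaction already attributed to the drug. Protocol 1.1.4 identifies injection-site reaction as the only known adverse drug reaction and reports that none was serious. A posted table of non-serious events that misses nearly all of them would be a poor public record of tolerability in primary care. The primary LDL-C analysis is not affected.

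**Working it through.** **Step 1. Compare the collection rule with each planned table.**

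| SAP table | What the collection rule can supply | Consequence |
|---|---|---|
| All TEAEs (2.7.1) | Every treatment-emergent SAE, plus AEs leading to discontinuation | Mislabelled and incomplete, not near zero |
| Non-serious TEAEs for registries (2.7.1) | Essentially only non-serious AEs leading to discontinuation | Severely incomplete |
| AESIs (2.7.1.1) | Serious hepatic and diabetes events, plus those leading to discontinuation | Serious part covered; non-serious part severely incomplete |
| SAEs; AEs leading to discontinuation | Collected as defined | No problem |

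**Step 2. See when a non-serious event can qualify.** Doses are given on Day 1 and Day 90 only (Protocol 6.5.2) and follow-up ends at Day 270. From the second dose onward no dose remains to be stopped. That period is 270 − 90 = 180 days, or 180/270 = two thirds of follow-up, in which a non-serious event has almost no route into the dataset.

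**Step 3. Reproduce the documents' figures (Protocol 1.1.4).**
- Any injection-site TEAE, phase III, inclisiran: 150/1833 = 8.18% (stated 8.2%). Placebo: 33/1822 = 1.81% (stated 1.8%).
- Clinically relevant injection-site TEAEs, phase III, inclisiran: 91/1833 = 4.96% (stated 5.0%).
- Clinically relevant reactions after the first dose, phase II: 3.5% as stated.
- Serious injection-site TEAEs on inclisiran in phase III: none.
- Withdrawals: "Four (4) inclisiran-treated subjects withdrew from study drug due to non-serious TEAEs at the injection site". That is 4/1833 = 0.22%, and 4/150 = 2.7% of those with such an event.

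**Step 4. Apply them to the 600 participants assigned to inclisiran (2 × 300).** Expected = 600 × event rate. Captured = 600 × 4/1833 = 1.31, because no such event was serious and discontinuation is the only remaining route. Under-count = 1 − captured/expected.

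| Benchmark | Rate | Expected in 600 | Captured | Under-count |
|---|---|---|---|---|
| Phase III, any injection-site TEAE | 8.2% | 49.1 | 1.3 | 97% |
| Phase III, clinically relevant | 5.0% | 29.8 | 1.3 | 96% |
| Phase II, after first dose | 3.5% | 21.0 | 1.3 | 94% |

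The exact 95% interval for 4/1833 is 0.06% to 0.56%, or 0.4 to 3.3 captured participants in 600. The chance of capturing none is (1 − 4/1833)^600 = 0.27. The percentage under-count does not depend on the 600, since both counts scale with it.

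**Step 5. Check whether the AESI shortfall can be sized.** It cannot. The documents give no expected rate for hepatic or diabetes events, nor the share that would be serious or lead to discontinuation. The injection-site calculation does not transfer to them.

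**The case against.** The strongest reply is that the restriction is not hidden. It is in Protocol 10.2, in the protocol summary and, for laboratory findings, in SAP 2.7.3. The SAP introduction says the data will be analysed according to Protocol section 12, whose AE tables are already restricted. On that view the fault is loose SAP wording. This largely stands, and it is why the remedy is mainly relabelling. It does not dispose of the point, because a programmer works from SAP 2.7.1 and a registry reader sees neither document.

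Two further replies stand:
- All SAEs are collected from consent to 30 days after the EOS visit (Protocol 10.3.3). A reader might infer that every TEAE and AESI rate will be falsely near zero. The documents do not support that, since serious events are in those tables.
- SAP 5.4 already plans to present whatever liver tests the EMR yields, and Table 5-1 sets HbA1c criteria. The hepatic and glycaemic questions are therefore not left wholly to the AE dataset.

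There are also minor routes for other non-serious events. Volunteered AEs may be detected (Protocol 10.2), and misuse or abuse goes on the AE form regardless (Table 10-1). Neither amounts to systematic collection.

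On MedDRA, a reader might infer that the AESI search will run in a different version from the coding. The documents do not show this: they give no lock date or lock version. What they show is a fixed version in SAP 5.3 beside at-lock rules in SAP 2.7.1.1 and 5.2.

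**Conclusion.** The SAP claims more than the collection rule can deliver. The registry table of non-serious TEAEs would be severely incomplete: for injection-site events, about 1.3 participants captured against roughly 21 to 49 expected in 600, an under-count of 94% to 97%. The non-serious part of the AESI table shares the defect, by an amount that cannot be computed. The all-TEAE table would in effect be a table of SAEs and AEs leading to discontinuation under a broader title.

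The range assumes that the cited inclisiran studies apply here. Phase III gave four doses with follow-up to day 540, against two doses over 270 days here, so 8.2% is an upper benchmark and a single figure of 97% would be too firm. The capture figure rests on four withdrawals in that longer schedule. It would also be going too far to say that readers will conclude such events are absent, or that hepatic and diabetes events are under-counted to the same degree; nothing in the documents supports either.

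**What to change.** 1. Bring the SAP 1.2 endpoint and the SAP 2.7.1 table list into line with Protocol 12.5.2, and remove incidence of TEAEs in general from the endpoint.
2. Title every AE, AESI and registry table 'SAEs and AEs leading to study-treatment discontinuation only'. State in the CSR and in the registry entry that other non-serious AEs were not systematically collected.
3. Reconcile version 25.0 in SAP 5.3 with the at-lock rules in SAP 2.7.1.1 and 5.2.
4. Optionally, present the EMR liver tests and HbA1c descriptively by randomised arm, with the number tested per arm. Use only values dated after baseline. Table 8-1, footnote 2, takes the closest HbA1c record before the EOS visit, which may predate baseline. State that testing is opportunistic and may differ by arm in an open-label trial, so these summaries supplement the AESI table and do not estimate incidence. Use randomised participants for this step, because the Safety Set requires a dose of study treatment, which the glossary defines as inclisiran.

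Items 1 to 3 cost wording and table titles. Item 4 costs some programming on data already extracted. None needs new data collection.
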